Title: Seizure Prophylaxis in Aneurysm Repair (SPAR)

Principal Investigators:

[name], B. [name], [name]

OVERVIEW

Research Objectives:

To examine the utility of levetiracetam (UCB Pharma, Brussels, Belgium) for seizure

prophylaxis in patients undergoing surgical repair of ruptured and unruptured intracranial

aneurysms.

Hypothesis:

No difference exists in seizure frequency post-aneurysm treatment between the levetiracetam and

no levetiracetam groups.

Background information and Rationale:

Seizures are a potential complication of surgical repair of intracranial aneurysms. In order to

prevent seizures, many surgeons administer prophylactic anti-epileptic medications during the

intra-operative and post-operative period; however, such practice is not supported by clinical

data [Raper et al]. A recent retrospective review found that the incidence of postoperative

seizures following intracranial aneurysm surgery was actually higher in those who received anti-

epileptics versus those who did not [Raper et al.]. Given the retrospective nature of this study, it

1

is not certain that both groups were equally at risk for seizures. Older retrospective studies have also suggested that antiepileptic prophylaxis confers no benefit [Sbeih et al., Rhoney et al.]. Recent information on patients undergoing surgery for supratentorial brain tumors has also cast some doubt on the efficacy of seizure prophylaxis. A recent trial randomized 123 patients undergoing craniotomy for resection of supratentorial tumors to either perioperative seizure prophylaxis with phenytoin or no seizure prophylaxis [Lang et al]. These investigators found that prophylactic use of anti-epileptic medication did not reduce the risk of perioperative seizures and was associated with an increased risk of adverse events. They suggested that the routine use of prophylactic anti-epileptic medications in that population may not be indicated.

The strongest argument in favor of routine use of anti-epiletic medications for patients undergoing craniotomy comes from older retrospective reviews that have suggested that rates of post-operative seizures decreased compared with historical controls following the implementation of prophylaxis [Ohman et al., Bidzinski et al.].

In 2009, an expert panel convened by the Stroke Council of the American Heart Association recommended against routine use of prophylactic anti-epileptic medication for patients with ruptured intracranial aneurysms due to lack of proven benefit [Bederson et al]. Although this group did not make any recommendations regarding the use of prophylactic anti-epileptic drugs during the surgical treatment of unruptured aneurysms, the risk of seizures, and therefore the potential benefits of seizure prophylaxis, appears to be lower in these patients compared with those with ruptured intracranial aneurysms Bederson et al., Baker et al]. Despite a lack of evidence for the use of anti-epileptic medication in preventing seizures in patients undergoing

microsurgical treatment of ruptured and unruptured brain aneurysms, the use of these medications remains common at many institutions including UMHS.

After a thorough review of the existing literature as well as a review of our own practice, the investigators have concluded that the decision to treat patients undergoing aneurysm repair with levetiracetam has reached true clinical equipoise. In other words, we cannot favor a decision to either administer or not administer this drug in these patients based on the existing information. The utility of anti-epileptic prophlaxis in the perioperative period for patients undergoing intracranial aneurysm repair remains a common practice that is not supported by the current literature that includes retrospective analyses as well as prospective trials for similar but not identical types of patients. We propose to settle this dilemma by performing a prospective randomized trial in patients undergoing aneurysm repair in order to definitively determine if the common practice of perioperative antiepileptic drug administration has any utility.

We have chosen to use levitiracetam as the medication for seizure prophylaxis for those patients who will randomize to perioperative seizure prophylaxis. Although phenytoin was the most common drug used for perioperative anti-seizure prophylaxis for many years, it has now been replaced by levetiracetam at many centers because of a perception that it is easier to administer and has fewer side effects [Zachenhofer et al, Milligan et al, Szaflarski et al., Lim et al]. The use of levetiracetam rather than phenytoin will reflect the practice pattern of most centers across the United States.

METHODS

Timeline: Prospective data for subjects will be collected on a secure file with password access for until up to 10 years after all data is published.

Inclusion/Exclusion criteria:

Inclusion:

- 1. Adult (≥18 years)
- 2. Presence of intracranial aneurysm (with or without rupture)
- 3. Patients with unruptured aneurysms must be recommended for microsurgery. Patients with ruptured aneurysms should be recommended for clipping or coiling.

Exclusion:

- 1. History of seizures within last 10 years
- 2. History of epilepsy
- 3. History of prior stroke
- 4. Currently prescribed medication with anti-epileptic activity (keppra, dilantin, tegretol, lamictal, topamax, etc.)
- 5. Brain tumor
- 6. Pregnant or nursing woman
- 7. Known levetiracetam allergy

Recruitment:

All patients seen at the University of Michigan Health System that meet inclusion criteria are currently seen by one of the investigators for routine clinical care. Prior to surgery, the study

will be explained to potential subjects and/or their legally authorized representatives by an investigator or a qualified study team member and they will be able to ask any questions that they may have. In addition, they may contact the PI (by phone, email, or mail). The investigators will recruit from their own patient population. No additional patient recruitment will be pursued.

Design:

Patients that meet all eligibility criteria will be randomized to either a "levetiracetam" or "no levetiracetam" group. There will be no attempt to "blind" the patient or caregivers with respect to group assignment. The group assignment will be known to the patient as well as relevant caregivers.

Patients in both groups will be treated according to all current reasonable clinical practices for the surgical treatment of intracranial aneurysms and its postoperative care. With the single exception of prophylactic levetiracetam administration to only one group, there will be no differences by design between the two groups with respect to treatment.

Those assigned to the "levetiracetam" group will receive a 500 mg intravenous dose during the operative case and then will be maintained on 500 mg orally twice a day for a total of seven days. Those patients that are assigned to the "no levetiracetam" group will receive no levetiracetam or any other anti-epileptic medications unless the treating physicians determine that such medications are clinically indicated based on specific circumstances. The use of any anti-epileptic medications will be recorded.

As is typical for all patients undergoing craniotomy for aneurysm repair, patients will be monitored in the neurological intensive care unit for at least one day following surgery. The

patients may then be transferred to a ward room where they will continue to be monitored according to standard clinical practices. If a subject is discharged prior to 7 days, periodic chart review and examination at routine clinical follow ups will be used to determine occurrence of seizure. If a seizure occurs in any patient, the seizure will be treated according to best clinical practices as determined by the treatment team without any regard to the patient's group assignment in the study.

A dataset will be prospectively assembled on each patient included in the study. Recorded information will include patient age, gender, location of aneurysm, size of aneurysm, duration of surgery, surgeon's assessment of degree of brain retraction during surgery (on a 3 point scale: less than average, average, more than average), the surgeon's degree of cortical damage during surgery (on a 3 point scale: less than average, average, more than average), the occurrence of an intraoperative hemorrhage, the occurrence of any other unexpected intraoperative events, the dose of levetiracetam and the duration of administration, any side effects or possible side effects of levetiracetam, the dose and duration of administration of any other anti-epileptic medications, the occurrence of any seizures including the number of such events, their duration, their treatment, and their sequelae if any.

Assessments will occur at routine care follow-up visits. These visits typically occur at 1-2 months, 4-6 months, and 6-12 months and up until 5 years +/- 6 months after surgery. Clinical data collected at these visits, specifically, the incidence of seizures, will be used for the study. Additionally, the study team may follow up on any previously reported adverse events.

The final assessment of clinical outcome will be made at the time of the regularly scheduled post-surgical outpatient appointments with the surgeon. At that time, the patient data will be de-

identified and entered into the registry. The study team will contact the patient via the telephone to try to obtain their 5-year clinical status.

The patient may be withdrawn from the study at any time if the treating physician or patient does not believe it is in the patient's best interest to continue to participate. All such instances will be recorded.

INFORMED CONSENT

When patients are seen in their physician's clinic for standard clinical care, the study will be explained to them by their physician (a study team investigator) or another qualified study team member and they will be able to ask any questions that they may have. In addition, they may contact the PI (by phone, email, or mail). Patients with ruptured aneurysms will be seen by a study investigator and informed consent may be obtained by an investigator or other qualified study team member.

An attempt will be made by the study team to contact previous participants via telephone to obtain their health status. In this case, a comprehensive telephone consent will be used to collect this information and the interaction will be recorded and maintained in the subject's study record.

PROCEDURES FOR MAINTAINING CONFIDENTIALITY

Data Security: Subjects will be given an ID number after being enrolled in the trial. Their ID number will be used on their data collection sheets. A linkage file will be maintained with patient identifiers to enable the study team to conduct chart reviews to extract data and monitor adverse events. Patient information will be de-identified prior to entry into the database. The database will be password-protected. The linkage file will be maintained in a secure, electronic database

for ten years following the close of the study. At that time, patient identifiers other than study ID will be destroyed.

ASSESSMENT OF RISKS AND BENEFITS

Risks:

Levetiracetam will not be given to half of the study subjects. Although levetiracetam is often used in these patients for seizure prophylaxis, its utility has never been established. A recent randomized trial found that prophylactic administration of antiepileptic medications in those undergoing routine craniotomy for tumor did not reduce the risk of seizures in that population. Therefore levetiracetam administration should not be considered standard treatment and withholding this medication falls within the scope of reasonable clinical practice.

Levitiracetam is associated with side effects in some cases. A recent trial of levitiracetam prophylaxis found that 1 patient had an adverse drug reaction out of 105 patients that were treated with this drug in the perioperative period [Milligan et al].

As with most anti-epileptic medications, levetiracetam appears to have some teratogenic potential. This potential appears to be dose dependent. All women of child-bearing age will undergo pregnancy testing prior to treatment per UMHS routine care practices. Pregnant women will be excluded from this study and will be treated according to standard practices of the treating physician.

There is a risk of loss of confidentiality. This risk is considered minimal and will be reduced by the maintenance of only de-identified data sets on password protected files.

Benefits: Participating subjects may benefit from increased monitoring by the study team as participants in the trial. Subjects in the levetiracetam group may benefit from reduced incidence of seizure. Subjects in the no levetiracetam group may benefit from a reduced indicence of side effects. Additionally, the study will yield important information to the community of physicians and researchers, and ultimately their patients; thus, there will be benefits to society.

ANALYSIS OF DATA

The two groups will be compared to verify that no significant differences in group composition were present. The treatment and no treatment groups will then be compared with respect to the occurrence of seizures including their frequency and duration. The treatment and no treatment groups will be compared with respect to the occurrence of levetiracetam side effects or possible side effects. Significance will be determined at p<0.05.

Up to 100 subjects will be recruited for this study. An interim analysis maybe conducted at any time during this study.

References:

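### The trial promises a definitive answer on utility, but p<0.05 in at most 100 patients cannot support its hypothesis of no difference, and the plan does not say how p≥0.05 will be read

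*Combined protocol and SAP*

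**What the plan says.** Under Research Objectives, the aim is "To examine the utility of levetiracetam (UCB Pharma, Brussels, Belgium) for seizure" prophylaxis in aneurysm repair, which is compatible with estimation. Under Hypothesis there is one statement: "No difference exists in seizure frequency post-aneurysm treatment between the levetiracetam and" no-levetiracetam groups. It is not labelled as a null, and no alternative is given.

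Background information and Rationale goes further: "We propose to settle this dilemma by performing a prospective randomized trial", and this is done "in order to definitively determine if the common practice of perioperative antiepileptic drug administration has any utility".

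In ANALYSIS OF DATA, the arms are to be "compared with respect to the occurrence of seizures including their frequency and duration", and also "compared with respect to the occurrence of levetiracetam side effects or possible side effects". The rule is "Significance will be determined at p<0.05". On size: "Up to 100 subjects will be recruited for this study". That section names no test, effect estimate, confidence interval, margin, target effect or power, and does not say what will be concluded if p is 0.05 or more.

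**The concern.** A significance test of equality is asymmetric. A small p-value is evidence against equality, but a large one may mean either that there is no effect or that the trial was too small to see it. Here the stated hypothesis is equality and the promised product is a definitive verdict on utility, so the result that agrees with the hypothesis is the one the criterion cannot establish.

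If p≥0.05 were written up as the hypothesised absence of difference, an inconclusive trial could be taken as evidence against prophylaxis. The plan contains nothing to prevent that. It also describes its baseline comparison as verifying that the groups do not differ significantly, which already uses non-significance as evidence of sameness.

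**Working it through.** **Inputs from the document.** Maximum total 100 (ANALYSIS OF DATA). The Risks section says half the subjects will not receive levetiracetam, so at most about 50 per arm. Threshold 0.05 (ANALYSIS OF DATA).

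**Assumptions, because the document is silent.** Two-sided testing; Fisher's exact test or the uncorrected chi-square test; outcome taken as at least one seizure per patient; seizure rate without levetiracetam of 5% to 20%. The plan has no power calculation to reproduce.

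**Step 1: precision when the arms look identical (no rate assumed).** With n = 50, z = 1.96 and observed proportion p, the Wilson limits are [p + z²/2n ± z√(p(1−p)/n + z²/4n²)] / (1 + z²/n). For equal observed proportions with Wilson limits l and u, the Newcombe half-width for the difference is √[(p−l)² + (u−p)²].

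For 5/50: centre (0.1 + 0.0384)/1.0768 = 0.1285; half-width 1.96 × √(0.0018 + 0.000384)/1.0768 = 0.0851; so l = 0.0435 and u = 0.2136. The difference then has half-width √(0.0565² + 0.1136²) = 0.127.

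The same steps give 0.099 for 2/50 in each arm and 0.157 for 10/50 in each arm. Perfect agreement therefore leaves limits of about ±10, ±13 and ±16 percentage points.

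**Step 2: chance of p≥0.05.** Sum Bin(a; 50, p₁) × Bin(b; 50, p₂) over all 51 × 51 tables whose p-value is at least 0.05. Results are percentages, Fisher / chi-square:

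| Rate without drug | No effect | Halved | 75% reduction | Complete prevention |
|---|---|---|---|---|
| 5% | 99.3 / 95.7 | 98.8 / 92.5 | 97.9 / 86.8 | 96.2 / 76.0 |
| 10% | 98.2 / 94.9 | 93.7 / 85.5 | 84.1 / 67.5 | 61.6 / 25.0 |
| 15% | 97.6 / 94.5 | 87.6 / 77.4 | 66.5 / 49.6 | 21.9 / 4.6 |
| 20% | 97.2 / 94.8 | 80.5 / 69.7 | 49.2 / 33.6 | 4.8 / 0.6 |

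**Step 3: what p≥0.05 tells the reader.** Divide the no-effect column by the halving column. By chi-square the ratio is 95.7/92.5 = 1.03 at 5%, 94.9/85.5 = 1.11 at 10% and 94.8/69.7 = 1.36 at 20%. By Fisher it is 99.3/98.8 = 1.01, 98.2/93.7 = 1.05 and 97.2/80.5 = 1.21. A ratio of 1 means that p≥0.05 does not discriminate at all between no effect and a halving.

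**Step 4: could the interval itself support no useful benefit?** Under true equality, the mean Newcombe half-width is 10.3, 12.5, 14.2 and 15.6 points at rates of 5%, 10%, 15% and 20%. The upper limit for benefit falls below half the rate in 6.0%, 10.5%, 17.2% and 23.3% of trials. Half the rate is an illustrative margin only; the document gives none.

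**Step 5: test and interval can disagree about zero.** With 4/50 without the drug and 0/50 with it, chi-square gives p = 0.041 but the Newcombe interval is −0.6 to 18.8 points. With 5/50 and 0/50, Fisher gives p = 0.056 although the interval is 0.9 to 21.4 points; chi-square gives p = 0.022, so that table is non-significant by Fisher only. Disagreement reaches about 18% of trials under complete prevention from a 10% rate. Any reporting rule must therefore say which prevails.

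**The case against.** The strongest reply is that the Hypothesis is the ordinary wording of a null, that p<0.05 is the matching test, and that the definitive language sits in the rationale and not in the analysis instructions. The formal objective is modest. On this view the plan omits an interpretation rule but contains no wrong rule.

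Much of that stands, and it lowers the severity. It does not remove the point: read as a null, the hypothesis can be rejected by this trial, but failure to reject it with about 50 per arm still does not deliver the definitive answer that the rationale promises.

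Three stronger readings are tempting, and the document does not support them:

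- A reader might infer that p≥0.05 will be reported as no utility. The plan never says so; it is silent.
- A reader might infer that the trial cannot show any benefit. Complete prevention from a 15% or 20% rate would usually be detected by either test, and from 10% in 75% of trials by chi-square.
- A reader might infer that this is an equivalence trial that must be enlarged. No equivalence design is declared, and the stated objective can be met by estimation at the present size.

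It is also fair to say that every detection percentage rests on assumed rates. The interval widths in Step 1 do not.

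**Conclusion.** The point holds and should be fixed, but it is not a fatal flaw. The hypothesis, the promise in the rationale and the p-value criterion do not fit together, and the result the plan leaves uninterpreted is the likely one: at assumed rates of 5% to 20%, p≥0.05 occurs in about 95% to 99% of trials if the drug does nothing and in about 70% to 99% if it halves seizures. A 75% reduction is missed in 87% to 98% of trials at a 5% rate and still in 34% to 49% at 20%. Only near-complete prevention from a rate of about 15% to 20% would usually be detected whichever test is used.

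These figures take the full 100 patients, equal arms and two-sided testing. The 100 is a cap, so a smaller trial would be less informative.

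**What to change.** Keep the sample size and change the wording and reporting.

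1. **Hypothesis.** Label the statement of no difference as the null hypothesis to be tested.
2. **ANALYSIS OF DATA.** Add that:
   - the main seizure result is the between-group difference in the proportion of patients with at least one seizure, with its 95% confidence interval, over a time window fixed before analysis;
   - the p-value and interval will come from matching methods fixed before analysis or, if they disagree about zero, the interval governs in both directions;
   - p≥0.05 alone, or an interval that includes zero, is inconclusive and will not be reported as no difference or no utility.
3. **Background information and Rationale.** Replace the promise to determine utility definitively with a statement that the trial will estimate the effect. Give the expected interval half-width: about 10 to 16 points at assumed rates of 5% to 20% if there is no difference.

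Any conclusion of no useful benefit would need a clinically justified margin fixed before analysis. The plan should admit that 100 patients would seldom meet one: 6% to 23% of trials under true equality for a margin of half the rate, at rates of 5% to 20%.

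The cost is a more modest stated claim. No patients, visits or data items are added.

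### The protocol ties seizure risk to rupture status but plans no stratified or adjusted comparison, and its baseline significance check can miss a chance imbalance of 16 points or more unless the ruptured share is extreme.

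*Combined protocol and SAP*

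**What the plan says.** In the combined protocol and SAP, Background information and Rationale says of unruptured aneurysms that the risk of seizures "appears to be lower in these patients compared with those with ruptured intracranial aneurysms". The inclusion criteria admit both ruptured and unruptured aneurysms. On allocation, the Design section says "Patients that meet all eligibility criteria will be randomized to either" of two groups, and describes no stratification, blocking or minimisation. Its list of recorded variables names aneurysm location and size but not rupture status.

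Analysis of Data begins with the baseline check: "The two groups will be compared to verify that no significant differences in group composition were present". It does not name the test or say what follows if a difference is found. The next step is the outcome comparison: "The treatment and no treatment groups will then be compared with respect to the occurrence of seizures including their frequency and duration". No stratum or covariate is mentioned. The significance level is 0.05 and the maximum enrolment is 100.

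**The concern.** The investigators name a prognostic factor and plan to guard against imbalance, but the tool they chose cannot do that job. Randomisation balances rupture status on average. What remains is chance imbalance in the one trial that is run, and at 50 patients per arm a significance test has little ability to see it. A pass does not verify balance. Even a correct pass or fail leaves the seizure comparison unchanged, because no adjustment follows.

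If one arm happens to hold more ruptured aneurysms, the crude seizure difference carries part of that excess, and readers would have been told that the groups did not differ significantly. The effect could point either way. It could mimic a drug effect or mask one.

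**Working it through.** The plan gives no ruptured share, seizure rates or power figure, so there is no stated figure to reproduce.

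**Inputs from the document.** At most 100 patients; half receive no levetiracetam (Assessment of Risks and Benefits), so 50 per arm at full enrolment; p<0.05.

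**Assumptions.** Two-sided tests; total number ruptured R from 10 to 90; ruptured/unruptured seizure risks pR/pU of 10/5, 15/5, 20/5 and 30/5%.

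**1. What the check misses.** With R = 50:
- 29/50 vs 21/50 (16 points) gives p = 0.110 by uncorrected chi-square and 0.161 by Fisher, so it is missed by both.
- 30/50 vs 20/50 (20 points) gives p = 0.046 and 0.071, so it is missed by Fisher only.

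**2. How often.** With R ruptured among 100 and 50 per arm, the number ruptured in one arm is hypergeometric(100, R, 50). Summing over splits of at least 16 points:

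| R | any test result | unflagged, chi-square | unflagged, Fisher |
|---|---|---|---|
| 50 | 16.1% | 9.0% | 13.4% |
| 40 or 60 | 15.3% | 8.7% | 12.8% |
| 30 or 70 | 12.6% | 7.7% | 7.7% |
| 20 or 80 | 7.8% | 0% | 5.6% |
| 10 or 90 | 1.6% | 0% | 0% |

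**3. Shift in the seizure difference at 29 vs 21, no drug effect.** The expected crude difference is (29/50 − 21/50) × (pR − pU) = 0.16 × (pR − pU). The standard error uses arm risks p1 = 0.58pR + 0.42pU and p2 = 0.42pR + 0.58pU: SE = √{[p1(1−p1) + p2(1−p2)]/50}. For 20/5%, p1 = 0.137 and p2 = 0.113, so SE = √[(0.1182 + 0.1002)/50] = 6.61 points.

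| pR/pU | shift (points) | SE (points) | shift/SE | 95% half-width (1.96 × SE) |
|---|---|---|---|---|
| 10/5% | 0.8 | 5.27 | 0.15 | 10.3 |
| 15/5% | 1.6 | 6.00 | 0.27 | 11.8 |
| 20/5% | 2.4 | 6.61 | 0.36 | 13.0 |
| 30/5% | 4.0 | 7.59 | 0.53 | 14.9 |

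Across all randomisations with R = 50 the mean absolute imbalance is 7.92 points. The mean absolute shift is therefore 0.0792 × (pR − pU) = 0.4, 0.8, 1.2 and 2.0 points.

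**4. False positives given 29 vs 21, no drug effect** (exact enumeration; toward the arm with more ruptured patients + the other direction = two-sided total):

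| pR/pU | chi-square | Fisher |
|---|---|---|
| 10/5% | 3.18 + 1.59 = 4.77% | 1.00 + 0.43 = 1.43% |
| 15/5% | 4.30 + 1.24 = 5.54% | 1.64 + 0.38 = 2.02% |
| 20/5% | 5.38 + 0.96 = 6.34% | 2.28 + 0.31 = 2.59% |
| 30/5% | 6.80 + 0.50 = 7.30% | 3.61 + 0.19 = 3.80% |

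The nominal rate is 2.5% per side. Averaged over all splits with R = 50, the two-sided rate is 4.6, 5.1, 5.4 and 5.4% by chi-square, and 1.4, 1.8, 2.1 and 2.6% by Fisher.

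**5. The stratified alternative at the same split.** Each stratum holds 50 patients divided 29 and 21, so the two Mantel-Haenszel weights are equal and the estimate is the mean of the two within-stratum differences. Its expectation is 0 under no effect. Write S = pR(1−pR) + pU(1−pU). The variance is ¼(1/29 + 1/21)S = 0.02053 S, against S/50 = 0.02 S for the crude difference. The ratio of standard errors is √(0.02053/0.02) = 1.013. In simulation (400,000 runs per scenario) the bias was 0.0 points and the Cochran-Mantel-Haenszel test rejected in 2.3 to 2.6% on each side. Power for a halved risk, averaged over splits, was 11.1, 14.7, 18.3 and 26.6%, against 11.0, 14.3, 18.3 and 26.6% for the crude chi-square.

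**The case against.** The strongest reply is that chance imbalance is already part of an unadjusted test's error rate, so the planned analysis is valid. That is right. Averaged error is near or below nominal, and the mean shift of 0.4 to 2.0 points is small beside confidence half-widths of 10 to 15 points. The 29 vs 21 split is also an unfavourable case: with 50 ruptured, an unflagged imbalance of 16 points or more arises in about one trial in eleven (chi-square) or one in seven (Fisher).

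The size also depends on assumed inputs. The document says only that risk appears lower and gives no rates. If Fisher's test were used for seizures, the two-sided false-positive rate given 29 vs 21 stays below 5% in every scenario. Its rate toward the heavier arm exceeds 2.5% only at 30/5%, a sixfold risk ratio that nothing in the document supports. With a ruptured share of 10% or 90%, neither baseline test misses 16 points.

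Finally, the analysis section is a short outline, so the unadjusted comparison is inferred from what it leaves out. Rupture status bears on eligibility and must be known at enrolment, even though the list of recorded variables does not name it.

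All of this limits the importance of the point and keeps it minor. It does not rescue the check, which cannot verify balance and has no consequence for the analysis. Leaving adjustment to be chosen later is a poor alternative in an open-label trial that allows an interim analysis at any time.

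**Conclusion.** The concern holds, as a minor one. The only safeguard described for a prognostic factor that the protocol itself names is a baseline significance test. At 50 per arm, that test can pass an imbalance of 16 points or more when the ruptured share is roughly 22% to 78% (chi-square) or 16% to 84% (Fisher), apart from a few totals near the ends of those ranges. The case for change is not that the planned analysis is invalid. A stratified comparison removes a shift of 0.8 to 4.0 points at a 16-point split, at almost no cost in precision or power.

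The result rests on full enrolment at 50 per arm, two-sided tests, and assumed ruptured shares and seizure risks. Because 100 is a maximum, a smaller trial could miss larger imbalances: with half the patients ruptured, the approximate detection threshold 1.96 × √[2 × 0.5 × 0.5/n] rises from 19.6 points at n = 50 per arm to 21.9 points at n = 40.

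**What to change.** 1. Hold rupture status in the dataset for every patient. Where it is missing, it can be recovered, since the confidentiality section provides that "A linkage file will be maintained with patient identifiers to enable the study team to conduct chart reviews to extract data".
2. Before outcomes are compared by arm, pre-specify any seizure (yes/no) over one stated window, analysed as a Mantel-Haenszel risk difference with 95% confidence interval and a Cochran-Mantel-Haenszel test, both stratified by rupture status. The Design section mentions a seven-day period ("If a subject is discharged prior to 7 days, periodic chart review and examination at routine clinical follow ups will be used") and long follow-up ("These visits typically occur at 1-2 months, 4-6 months, and 6-12 months and up until 5 years +/- 6 months after surgery") without naming either as primary. The investigators should fix one; the method works with either. This covers seizure occurrence only. The planned comparisons of frequency and duration need their own specification.
3. Replace the significance check with a descriptive baseline table by arm that includes rupture status.
4. Only if enrolment has not begun, also stratify randomisation by rupture status, with concealed, varying block sizes.

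The cost is one data field, slightly more analysis, and about 1.3% more standard error at a 16-point split. Step 4 adds a second concealed randomisation list. No extra patients or procedures are needed.
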